selected hospitals to the research team. **Step 4** involves the research team randomizing the available hospitals to either the intervention group or waitlist control group. Randomization will be stratified based on the number of overnight beds from the most recently available count available from NHS England (dichotomized at the medium, to create “large” and “small” hospitals).³² **Step 5** involves the research team emailing the randomized lists back to the Making Data Count team to commence scheduling. If the original list contains fewer than 20 hospitals, then the Making Data Count team will continue recruitment and another list of hospitals will be sent to the research team to randomize in the same stratified manner each month. The purpose of this is pragmatic – to ensure trainings can commence in a timely fashion, alongside the research being conducted.

Figure 3. Five steps in the selection and randomization process

Scheduling training

Hospitals allocated to the intervention group will be invited to schedule training over an initial five-month period. Hospitals allocated to the waitlist control group will be invited to schedule a training over a later five-month period. A hypothetical training schedule appears

in Figure 4. Approximately two hospitals may receive training each month, but the schedule will ultimately depend on hospital availability and training capacity.

[figure not shown]
Figure 4. Example of potential schedule

Scheduled Training Order	Group 1 - Intervention
Month 1	Hospital A
Month 1	Hospital G
Month 2	Hospital D
Month 2	Hospital F
Month 3	Hospital C
Month 3	Hospital I
...	...
Group 2 – Waitlist	
Month 6	Hospital K
Month 6	Hospital L
Month 7	Hospital J
Month 7	Hospital B
Month 8	Hospital H
Month 8	Hospital E
...	...

Selection of board papers from hospitals

From each hospital, two board papers will be retrieved for a total sample of 40 papers. For the hospitals in the intervention group, we will retrieve the papers published in the nearest month before the intervention was delivered (pre-intervention observation) and approximately five months after the intervention was delivered (post-intervention observation). This selection process is represented in the top half of Figure 5. As boards do not publish their papers every month, it is not always possible to sample precisely one month pre-intervention or five months post-intervention.

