the board papers (the denominator), for pre-intervention and post-intervention periods. To determine the absolute effect of the intervention we will compare the proportions of charts presented as SPC charts (between intervention and control arms) for each hospital and adjust for the proportion of SPC charts in the pre-intervention period. These differences will be compared between waitlist and intervention hospitals using a t-test and reported with 95% confidence intervals (a log transformation will be used if appropriate). To determine the relative effect (risk ratio) of the intervention, we will fit a zero-inflated negative Binomial regression model (outcome data are likely to be over-dispersed with a high number of zero counts), with the outcome of the number of SPC in the post-intervention period, fixed categorical effects for the intervention and the proportion of charts which were SPC charts in the pre-intervention period, and an exposure of the number of charts (in the post-intervention period). The offset here acts much like a denominator representing the number of opportunities each chart could have been depicted in an SPC format.

A sensitivity analysis based on the per-protocol group allocations will be performed if necessary. The remaining outcomes will be reported using descriptive statistics, e.g., counts, percentages, medians, and interquartile ranges. We will describe the proportion of control charts displayed as icons versus the full control chart.

Analysis of data from feedback forms.

Likert scale responses to each question on the feedback form will be described using medians and interquartile ranges. For the free-text responses, the number of positive, negative, and neutral comments will be reported. In addition, the available free-text responses will be thematically analyzed according to Braun and Clarke's method to reveal ways to improve future training or reasons others may (or may not) want to take it up.³⁴

Ethical considerations

This research has received ethical approval to conduct from the University of Warwick Biomedical and Scientific Research Ethics committee (BSREC 100/20-21). The research team declares no conflicts of interest to disclose. The research team will work closely with NHS Improvement's Making Data Count team to design and conduct the study, and their support will be acknowledged in the final manuscript. NHS Improvement will have no role in the analysis, interpretation of data, or in writing the manuscript.

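### The absolute-effect t-test omits the bed-size stratum used in randomisation, a possible loss of precision; its undefined log option would also change the effect measure if used.

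*Combined protocol and SAP*

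**What the plan says.** **Randomisation** (Selection and randomization of hospitals, Step 4): "Randomization will be stratified based on the number of overnight beds", split into large and small hospitals. If the first list holds fewer than 20 hospitals, Step 5 adds that "another list of hospitals will be sent to the research team to randomize in the same stratified manner each month".

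**Absolute effect** (Planned Analyses, Analysis of data from board papers): the paragraph opens "To determine the absolute effect of the intervention". It compares the arms on the proportion of charts that are SPC charts and will "adjust for the proportion of SPC charts in the pre-intervention period". Then: "These differences will be compared between waitlist and intervention hospitals using a t-test and reported with 95% confidence intervals". A parenthesis adds that "a log transformation will be used if appropriate". The Abstract likewise names adjustment for pre-intervention use only. Bed numbers appear in the analysis section only as a descriptive characteristic.

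**Relative effect** (same paragraph): a separate zero-inflated negative binomial model is fitted "To determine the relative effect (risk ratio) of the intervention", because "outcome data are likely to be over-dispersed with a high number of zero counts". It has no bed-size term either.

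**Sizing** (Sample size calculation): at least 16 hospitals for a rise from 10% to 40%, that is 30 percentage points, with alpha 0.05, power 0.80 and r=0.90. Twenty are planned, 10 per arm.

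**The concern.** Stratifying by bed size balances it across the arms, so between-stratum variation cannot contribute to the difference between arms. A t-test without the stratum still leaves that variation in its error term. The standard error then overstates the true variability of the estimate, to the extent that bed size predicts the outcome beyond what baseline already explains. With 20 hospitals, a wider interval than the design warrants matters.

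The secondary issue is the log. The plan does not say when it would be appropriate, whether proportions or changes would be logged, or what happens to zeros. A zero proportion has no log, and neither has a zero or negative change. Zeros are expected: the plan says so for its count model, and hospitals are invited from the 75 whose board papers had no SPC charts (Problem description). A back-transformed log comparison is a ratio, whereas the sentence promises an absolute effect and the trial was sized on percentage points.

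**Working it through.** **1. The plan's own sample size.** Inputs from the Sample size calculation section: 10% vs 40%, alpha 0.05 (two-sided assumed), power 0.80, r=0.90.

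- Two-proportion formula, pooled p = 0.25: n = [1.960 × √(2 × 0.25 × 0.75) + 0.842 × √(0.09 + 0.24)]² / 0.30² = 31.5 per arm.
- With continuity correction: (31.5/4) × [1 + √(1 + 4/(31.5 × 0.30))]² = 37.9, so 38 per arm.
- Baseline factor 1 − r² = 0.19: 38 × 0.19 = 7.22, so 8 per arm and **16 in total**, as stated. Without the correction, 32 × 0.19 = 6.08 gives 7 per arm, 14 in total.

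The stratum does not disturb this. The documents give no between-hospital SD. Taking the one implied by the formula, √(0.25 × 0.75) = 0.433, the residual SD is 0.433 × √0.19 = 0.189. If bed size is irrelevant, the lost degree of freedom moves power for 30 points from 83.6% to 83.1% at 16 hospitals and from 91.7% to 91.5% at 20.

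**2. Cost of omitting the stratum.** Assumptions: 20 hospitals, 5 per arm in each stratum, normal residuals, baseline as covariate, r=0.90. R is the share of baseline-adjusted residual variance due to bed size. The documents do not give R, so a range is shown.

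In units of the residual variance, the stratum's sum of squares is 20R. About 1/18 of it is absorbed by the baseline term, and the rest stays in an error term with 17 degrees of freedom. The expected mean square is then (1 − R) + 20R × (17/18)/17 = 1 + R/9. With the stratum in the model it is 1 − R on 16 degrees of freedom. Hence

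width ratio ≈ (t₁₇/t₁₆) × √[(1 + R/9)/(1 − R)], with t₁₇/t₁₆ = 2.1098/2.1199 = 0.9952.

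| Assumed R | Formula | Simulated ratio (40,000 trials) | Type I error without stratum |
|---|---|---|---|
| 5% | 1.024 | 1.023 | about 4.5% |
| 10% | 1.055 | 1.054 | about 4.0% |
| 20% | 1.125 | 1.124 | about 3% |
| 30% | 1.209 | 1.210 | about 2% |

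With the stratum in the model, type I error stays near 5%. At R = 0 the model with the stratum has an interval about 0.6% wider at 20 hospitals and 1% wider at 16. If the bed-size effect is equal before and after training, a change score removes it and nothing is lost.

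**3. The log option.** Assumptions: 20 charts per paper, mean 10%, beta-binomial with intra-hospital correlation 0.3. In simulation this gives a pre-post correlation of about 0.90, matching the plan.

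- Zeros: with a = 0.1 × (1/0.3 − 1) = 0.233 and b = 2.1, P(0) = B(a, b + 20)/B(a, b) = 0.555. That is 20 × 0.555 ≈ 11 of 20 pre-intervention proportions. Under a plain binomial, P(0) = 0.9²⁰ = 0.122.
- Changes: about 8 of 10 control changes are zero or negative.
- Constant: 10% vs 40% is a 30-point difference and a ratio of 4.0. The logged analysis returns 10.4, 4.85 or 3.5 when 0.1, 0.5 or 1 chart is added.
- Illustrative dataset: four control hospitals at 0 and six at 1/6 (mean 10%); two intervention hospitals at 0 and eight at 0.5 (mean 40%). The raw t-test gives 30 points (95% CI 14.9 to 45.1, p=0.0006). Adding 0.01 before logging gives exp{[0.2 ln 0.01 + 0.8 ln 0.51] − [0.4 ln 0.01 + 0.6 ln 0.1767]} = 4.1, p=0.058. Adding 0.05 gives 2.8, p=0.018.

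**The case against.** **No bias, and no evidence that bed size matters.** Nothing in the documents links bed numbers to SPC use after baseline adjustment, and with r=0.90 baseline will absorb most stable size differences. The Limitations section says the study is powered for large effects and expects that more precision would not change its interpretation. This stands: the loss is conditional. It does not remove the case for analysing as randomised, because including the stratum costs so little if bed size is irrelevant.

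**The log is conditional.** The paragraph calls the quantity an absolute effect, and the fact that zeros cannot be logged is itself a reason not to invoke the option. A reader might infer that the log will replace the percentage-point difference; the text does not say so. What stands is that the trigger, the quantity to be logged and the zero rule are missing.

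**Error inflation.** A reader might infer that the open log inflates type I error. Taking the smaller p of the logged and unlogged versions, with 0.5 charts added, gives 6.1–6.5% under the assumptions in step 3, but about 0.7% at a mean of 2%. This is a worst case for an analyst who picks the smaller p, not a property of the plan.

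**Monthly lists.** Repeated small lists might suggest unbalanced strata and a liberal test. The documents give no rule for odd-sized lists and plan 10 hospitals per arm, so figures of that kind would rest on an invented rule and are not used here.

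**Conclusion.** The concern holds as a matter of precision and specification. The absolute-effect analysis ignores a factor used in randomisation. If bed size explains 5 to 30% of the residual variance, the 95% CI is about 2 to 21% too wide and type I error falls from 5% to between about 4.5% and 2%. These figures rest on an assumed share, balanced strata, normal residuals and r=0.90, so the loss is possible and not established. They do not support a claim that the estimate is biased or that 16 hospitals is the wrong minimum.

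The log is a smaller point. It cannot be applied to the expected zeros without a constant that the plan does not give, and if applied it would report a ratio in place of the percentage-point difference. Whether baseline enters as a change score or a covariate makes almost no difference when bed size is irrelevant (mean CI width 0.829 vs 0.835 SD), so that needs only a clear sentence.

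**What to change.** State the absolute-effect analysis as one linear model: post-intervention proportion on arm, pre-intervention proportion (continuous) and bed-size stratum as assigned at randomisation. Report the adjusted difference in percentage points with a 95% CI. Keep this unlogged difference as the main result whatever the distribution looks like. Limit any logged version to a sensitivity analysis, stating in advance what is logged and which constant is added. Ratios otherwise stay with the risk-ratio model; since that model also lacks bed size, say whether this is intended.

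This takes one paragraph of text and no new data. The stratum uses one degree of freedom, which costs about 0.6% in CI width at 20 hospitals and 1% at 16 if bed size is irrelevant. The unlogged analysis can have somewhat less power than a logged one: 85% vs 90% at 20 hospitals in one simulated setting, where intervention hospitals' post-training use was unrelated to baseline and the intra-hospital correlation was 0.3.

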Methods. A parallel cluster randomized trial (with baseline-line measurements) across 20 National Health Service (NHS) hospitals in England. The hospitals will be randomly split into two groups. One group will be scheduled to experience the training intervention, and the other group will be placed on a waiting list to experience the training later. The primary analysis will compare the difference in the use of indicated control charts between waitlist control and intervention hospitals (adjusting for pre-intervention use) reported with 95% confidence intervals. A qualitative thematic analysis of feedback forms will be conducted.

Discussion. The present research will evaluate the impact of the training intervention on the use of control charts. The results will apply to institutions that are non-early adopters of this training intervention.

Keywords: Quality Improvement, Data Visualisation, Change Management, Learning Health System, Inservice Training

INTRODUCTION/BACKGROUND

Problem description

The way data are presented can influence board members' decisions.² Statistical process control (SPC) charts provide a data-driven approach to guide decisions related to quality improvement.^{3,4} A previous study demonstrated that SPC charts are seldom used in National Health Service (NHS) hospital board papers in England,^{5,6} and inspired an NHS-Improvement/England (NHS I/E) (2019) initiative called 'Making Data Count.' Making Data Count aims to help NHS staff create and use SPC charts effectively.⁷ Starting in late 2017 this training was offered on a first-come, first-serve basis. As of April 2021, approximately 120 organizations have taken part. A non-randomized retrospective evaluation suggests that the training may be effective for early adopters,^{8,9} but whether these benefits extend to hospitals less eager to take part is uncertain.

NHS-Improvement's team reviewed published board papers for every hospital in England in 2020 (at the time 217) to determine what presentation format was predominately used in their board papers to present quality and safety metrics. Seventy-five hospital board papers lacked SPC charts. Rather, these board papers were predominantly composed of Red-Amber-Green (R-A-G) data presentations or two-point comparisons, e.g., year 1 vs year 2, neither of which are data-driven presentation methods for quality improvement.¹⁰

Available knowledge

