Based on our sample size calculation, a minimum of 16 hospitals with pre- and post-intervention measures is required to detect a 30-percentage point increase in the proportion of indicated SPC charts from 10% to 40% between control and intervention measures. The sample size was calculated with an alpha of 0.05 and a power of 0.80. Due to the study design (measurements taken of the outcome in a baseline period), adjustment for the correlation between pre- and post-intervention measures were made, estimated at $r=0.90$.³¹ The primary analysis will be conducted based on intention-to-treat. While only 16 hospitals are required, we have planned to include 20 on an ‘insurance principle’ in case some hospitals drop out.

Selection and randomization of hospitals

At the present time, SPC training cannot be mandated. The hospitals that take part will ultimately depend on their willingness and availability to experience training. The five-step selection and randomization process for hospitals is presented in Figure 3. **Step 1** involves obtaining contact information for all the hospitals identified as relying on R-A-G charts or two-point comparisons to present quality and safety performance metrics in their board papers (75 at the time the protocol is being written). **Step 2** involves the Making Data Count team inviting the hospitals to take up training over a specified 12-month period. As part of their informed consent, hospitals will be made aware that they may be offered training over either the initial 6-months or the later 6-months in a randomized fashion. **Step 3** involves selecting the 20 hospitals that first express an interest in taking up the training or a smaller number which do so after 30 days have passed (note that recruitment will continue until 20 express an interest – see Step 5). The Making Data Count team will email the list of

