Figure 5. Selected board papers retrieved from each hospital during the pre-intervention intervention and post intervention observation periods

Notes: The top box depicts the trusts that will experience the intervention (the intervention group), and the bottom box depicts trusts that will be placed on a waiting list to experience the intervention later (the control group). The black cells show the month of the training intervention. Green cells represent the month from which the pre-intervention papers will be retrieved, and the red cells represent the month from which the post-intervention papers will be retrieved.

For hospitals in the waitlist control group, we will form a matched list based on the order in which each is scheduled to receive training (earliest month) under the waitlist design. For example, the hospital in the intervention group scheduled to receive training first will be matched with the hospital in the waitlist group scheduled to receive training first, see the bottom half of Figure 5. This ordering is planned to minimize the possibility for waitlist hospitals to experience the training in the timespan planned for the current evaluation the waitlist control group's "post-observation" board papers will be selected from a month before each waitlist control hospital experiences training.

Outcome measures²

² The outcome measures were informed by the previous non-randomized studies discussed in the problem section and through conversations with trainers who designed the Making Data Count intervention.

Our data will be made publicly available for replication and further analyses. The main outcome measure will be the proportion of SPC charts indicated about quality and safety measures (the numerator) out of all quality and safety charts indicated in the board papers (the denominator). SPC icons will be added to the numerator and the denominator where they indicate that a unique control chart has been used but not included in the paper. Additional secondary outcome measures will be extracted from the board papers and feedback forms, as described below.

Data extraction from board papers

Quantitative measures for data contained in the board papers will be created by coding information within each board paper. Four independent reviewers (R1, R2, R3, R4) will conduct the coding over three steps.

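### The planned risk ratio is not fully defined, and the zero-inflated model's arm coefficient can differ from the ratio of overall SPC proportions

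*Combined protocol and SAP*

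**What the plan says.** Under Planned Analyses (Analysis of data from board papers), the main analysis has two pieces. The absolute effect is a baseline-adjusted comparison of hospital proportions by t-test. The relative effect is described as follows: "To determine the relative effect (risk ratio) of the intervention, we will fit a zero-inflated negative Binomial regression model". The reason given is that "outcome data are likely to be over-dispersed with a high number of zero counts". The outcome is the post-period count of SPC charts, with the post-period number of charts as exposure and "fixed categorical effects for the intervention and the proportion of charts which were SPC charts in the pre-intervention period". Read literally, that makes baseline a categorical term, but no cut-points are given.

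The text does not say which terms enter the inflation part, whether the risk ratio is the exponentiated count-part coefficient or a ratio of predicted overall means, or how its confidence interval is obtained. No other section supplies this.

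The outcome itself is an overall proportion (Outcome measures): "The main outcome measure will be the proportion of SPC charts indicated about quality and safety measures (the numerator") over all such charts. On the population, the Problem description says "Seventy-five hospital board papers lacked SPC charts", and Selection and randomization of hospitals invites "hospitals identified as relying on R-A-G charts or two-point comparisons to present quality and safety performance metrics". The sample size section plans for a "30-percentage point increase in the proportion of indicated SPC charts from 10% to 40" per cent. The Abstract (Methods) makes the difference in use the primary analysis.

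**The concern.** A zero-inflated negative binomial model splits hospitals into a class that always yields zero and a class that yields counts. The arm effect in the count part compares only hospitals outside the zero class. If training turns hospitals with no SPC charts into hospitals with some, that gain sits in the inflation part and is missing from the coefficient. In this trial such a route is plausible, because the plan expects many zeros and recruits from hospitals whose papers lacked SPC charts.

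Two analysts following the text could therefore publish different risk ratios from the same data. One of them could be close to 1 beside an absolute difference of 30 percentage points.

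**Working it through.** **The plan's own figure.** Two-sided alpha 0.05, power 0.80, 10% versus 40%, continuity-corrected: 38 per arm. The plan says that "adjustment for the correlation between pre- and post-intervention measures were made", with r = 0.90. The factor is 1 − 0.90² = 0.19, and 38 × 0.19 = 7.22, so 8 per arm or 16 hospitals. The stated minimum is reproduced, and it does not involve the zero-inflated model.

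**The identity.** Let π0 and π1 be the zero-inflation probabilities (control, intervention) and exp(β) the count-part arm effect, without covariates. Then

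overall ratio = exp(β) × (1 − π1)/(1 − π0).

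The two agree only if π1 = π0.

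**With the plan's 10% and 40%.** Write p0 = 1 − π0 and p1 = 1 − π1 for the shares outside the zero class, and m0 and m1 for the mean SPC share within that class. Then 0.10 = p0 × m0 and 0.40 = p1 × m1, so

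exp(β) = m1/m0 = (0.40/p1)/(0.10/p0) = 4 × p0/p1.

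The documents do not give π0 or π1. The values below are assumptions, and the overall ratio is 4.0 in every row.

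| π0 | π1 | 4 × p0/p1 | exp(β) |
|---|---|---|---|
| 0.5 | 0.5 | 4 × 0.5/0.5 | 4.0 |
| 0.5 | 0.2 | 4 × 0.5/0.8 | 2.5 |
| 0.5 | 0.1 | 4 × 0.5/0.9 | 2.2 |
| 0.7 | 0.2 | 4 × 0.3/0.8 | 1.5 |
| 0.75 | 0 | 4 × 0.25/1 | 1.0 |
| 0.2 | 0.5 | 4 × 0.8/0.5 | 6.4 |

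**Does the choice of inflation terms matter?** The model was fitted by maximum likelihood to simulated data: 20,000 hospitals per arm, 30 charts each, dispersion 0.2 (all assumed), no baseline term.

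| π0, π1 | Inflation part | exp(β) | Model overall ratio | Raw ratio |
|---|---|---|---|---|
| 0.5, 0.5 | arm | 4.01 | 3.95 | 3.95 |
| 0.5, 0.5 | constant | 4.01 | 4.01 | 3.95 |
| 0.5, 0.2 | arm | 2.52 | 4.07 | 4.07 |
| 0.5, 0.2 | constant | 2.57 | 2.57 | 4.07 |
| 0.6, 0.1 | arm | 1.78 | 4.01 | 4.01 |
| 0.6, 0.1 | constant | 1.82 | 1.82 | 4.01 |

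A constant inflation part does not protect. It forces π1 = π0, so both the coefficient and the model's overall ratio miss the raw ratio. With arm in the inflation part, the combined ratio recovers it, but the coefficient alone does not.

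**Direction.** Further large-sample simulations used a control pre/post correlation of about 0.90, a baseline term and 10 to 40 charts per paper (the chart range is assumed). With constant inflation the coefficient was 1.0 when training acted wholly by adoption (20% versus 80% of hospitals using SPC, each for half their charts). It was 2.5 to 2.8 in a mixed case, and 4.2 to 7.7 in two cases where 80% or more of control hospitals already used SPC. A single-part Poisson model gave 3.95 to 4.11 throughout.

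**The case against.** The strongest reply is that the relative effect is not the primary analysis. That is correct and limits the weight of the point.

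A second reply is that the listed effects may be meant for both parts of the model, and that a careful analyst would combine them. The text does not say so, and even on that reading the way the ratio is formed is missing.

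A third is that the coefficient is right if training leaves the zero class unchanged. That also stands: a discrepancy is possible, not certain. The coefficients above 4 with baseline adjustment arose only where most control hospitals already used SPC, which fits poorly with recruitment from hospitals whose papers lacked such charts.

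A fourth is that the gap is one of wording, so replacing the model is a preference. In part this stands: a properly combined zero-inflated estimate would answer the definitional point.

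The single-part model has limits of its own. In simulated 20-hospital trials with a true ratio of 4, its medians were 4.7 to 5.3. A leave-one-hospital-out interval is undefined when an arm has only one SPC-using hospital, because deleting it leaves that arm at zero. If a fifth of control hospitals use SPC (assumed), the chance of none among 10 is 0.8¹⁰ = 10.7%, and of exactly one is 10 × 0.2 × 0.8⁹ = 26.8%, together about 37.6%. With no effect and a fifth using SPC in both arms, the chance that either arm has none or one is 1 − (1 − 0.376)² = 61%.

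A reader might also infer that the zero-inflated model has a worse type I error than a Poisson model. The documents do not support that, since they state no interval method for the ratio. A comparison of Wald intervals from one model with jackknife intervals from the other changes two things at once and says nothing about the model alone.

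**Conclusion.** The point holds: the risk ratio is incompletely defined, and the most direct reading of the model output can differ materially from the ratio of the outcome the plan defines. The identity is exact. The values 4, 2 and 1 for an equal, doubled and quadrupled share outside the zero class need only the plan's 10% and 40%, ignoring covariates. All other figures rest on assumed zero shares, chart numbers and dispersion.

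A reader might infer that the trial's main conclusion or its size is at risk. It is not: the absolute difference comes from a separate t-test, and the minimum of 16 hospitals is reproduced without this model. A reader might also infer that the published ratio will be too low. The documents do not establish that, because they give no zero shares by arm. The point should be fixed, but it concerns the relative effect only.

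**What to change.** In Planned Analyses (Analysis of data from board papers):

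- Define the risk ratio as the ratio of overall SPC proportions, intervention versus waitlist, with zero-SPC hospitals included. State the weighting: a log-charts offset gives a chart-weighted ratio, whereas the t-test compares hospital-level proportions.
- Do not report the zero-inflated model's count-part arm coefficient as the risk ratio.
- Estimate the ratio with a single-part log-link model of the SPC count (log charts as offset) on arm and baseline SPC proportion. Enter baseline as continuous, and say that this changes the categorical wording.
- Take the p-value from a permutation test within bed-size strata and monthly randomisation list, using a statistic that stays finite when a permuted arm has no SPC charts.
- Give a leave-one-hospital-out jackknife interval (t on n − 3 degrees of freedom, 17 with 20 hospitals) only if each arm has at least two SPC-using hospitals. If an arm has only one, give the point estimate and permutation p-value without that interval. If either arm has none, report only the absolute difference.
- If the zero-inflated model is kept, put arm in the inflation part and report the ratio of standardised overall means, (1 − π) × μ. Alternatively, label exp(β) as a rate ratio among hospitals outside the zero class.

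The cost is one paragraph of analysis text and no new data. The price is an estimate that runs somewhat high with 20 hospitals and an interval that will often be unavailable if few hospitals use SPC.
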